4.3.5.1 Adverse events

Adverse events will be coded to a lower level term (LLT), PT, HLT, high level group term (HLGT) and primary SOC using the version of MedDRA in effect at Sanofi at the time of each database lock.

For patients' cohort, they will be classified into predefined standard categories according to chronological criteria:

- Pre-treatment AEs: AEs that occurred, worsened or became serious during the pre-treatment period defined as the time between informed consent signature and the first IMP administration.
- Treatment emergent AEs (TEAEs): AEs that occurred, worsened or became serious during the TEAE period defined as the time from the first IMP administration up to the EoT visit (EoT included).
- Post-TEAEs: AEs that occurred, worsened or became serious during the post-TEAE period defined as the time starting after the TEAE period (including the follow-up period).

Treatment-emergent AEs will be assigned to the treatment received at the time of the AE onset. If the onset date (or time) of an AE (occurrence, worsening or becoming serious) is incomplete or missing, then the AE will be considered as a TEAE unless a partial date (or time) shows it as a pre- or post-treatment event.

For all healthy volunteers, safety data will be considered as part of a single period starting with the signature of the informed consent and ending with the EoS visit (EoS included).

All AEs reported in the study will be listed, sorted by participant, onset date and time.

The following TEAEs summaries will be provided for the patients' cohort of the safety population:

- Overview of TEAEs: number and percentage of participants with any TEAE, any serious TEAE, any TEAE leading to death (if any occurred), any TEAE leading to permanent treatment discontinuation, and any TEAE of special interest.
- Summary of TEAEs by primary SOC and PT:
 - Number and percentage of patients with at least one TEAE.
 - Number of occurrences of TEAEs.

Patients presenting TEAEs will be listed sorted by primary SOC and PT. By definition, no TEAEs summary will be displayed for healthy volunteers. AEs that occur outside the treatment-emergent period or in healthy volunteers will be summarized separately.

In addition, the following listings/summary will be provided:

- Listing of any deaths and serious AEs.
- Listing of any AEs leading to permanent treatment discontinuation.

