4.3.5.2 Vital signs

Heart rate, systolic and diastolic blood pressures (SBP and DBP), body temperature and respiratory rate will be analyzed as raw parameter value and change from baseline.

Body weight will be analyzed as raw parameter value and percent change from baseline. BMI will be analyzed as raw parameter value.

Baseline definition

The values to be used as baseline will be the Day 1 (Visit 2, Week 0) predose assessment. If any of the scheduled baseline tests are repeated for any participant, the last rechecked values will be considered as baseline, provided, for patients, they were done before the IMP administration of the respective treatment phase, and in the same condition.

Abnormalities analyses

For vital sign parameters, analysis will be performed using all post-baseline assessments done during the TEAE period/safety period, including all unplanned and rechecked values. Counts of participants with potentially clinically significant abnormal (PCSA) values will be presented by cohort, regardless of the baseline status. PCSA values are defined as abnormal values considered medically important by the Sponsor according to predefined criteria/thresholds based on literature review and defined by the Sponsor.

A listing of individual data from participants with post-baseline PCSAs will be provided; values will be flagged when reaching the PCSA criteria.

PCSA criteria are detailed in [Section 8 \(Appendix D\)](#).

Descriptive statistics and plots

For heart rate, blood pressures, body temperature and respiratory rate, raw data and absolute changes from baseline will be summarized in descriptive statistics for patients' cohort and scheduled time of measurement.

For body weight, raw data and percent change from baseline will be summarized in descriptive statistics by cohort and scheduled time of measurement.

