Day	D-28 to D-1	D 1	D8 ±2 days	D15 ±2 days	D22 ±2 days	D29 ±2 days	D43 ±2 days	D57 ±3 days	D71 ±3 days	D85 ±3 days	D99 ±3 days	D113 ±3 days	D155 ±3 days	EoS D197 ±3 days	UNSCH		
Week		W0	W1	W2	W3	W4	W6	W8	W10	W12	W14	W16	W22	W28			
Visits	V01	V02	V03	V04	V05	V06	V07	V08	V09	V10	V11	V12	V13	V14			
Patient reported outcomes (PRO)																	
POEM			X	X	X	X	X	X	X			X	X	X	(X)	X	
CDLQI			X	X	X	X	X	X	X			X	X	X	(X)	X	
Worst itch NRS ^j	X	X	X	X	X	X	X	X				X	X	X	(X)	X	
Sleep disturbance NRS ^j	X	X	X	X	X	X	X	X				X	X	X	(X)	X	
Skin pain NRS ^j	X	X	X	X	X	X	X	X				X	X	X	(X)	X	
eDiary ^k	X	X	X	X	X	X	X	X				X	X	X	(X)	X	
Safety																	
AE/SAE collection	X	X	X	X	X	X	X	X	X	X	X	X	X	X	X	X	
Height			X									X		X		X	
Body weight	X	X										X		X		X	
Vital signs ^l	X	X		X		X	X	X			X		X	(X)		X	
Physical examination ^m	X	X ^m										X ^m		X ^m		X ^m	
Saliva swab sample ⁿ		X															
Optional assessments																	
Optional Biomarker research samples (blood) ^o			X									X					

- a For the purpose of this study, any female who has had her first menstrual period (menarche) and is sexually active will be considered to be of childbearing potential. Female patients who are not of childbearing potential at the start of the study but have the onset of menarche during the course of the study and are sexually active will also have to follow adequate birth control methods to continue participation in the study. These females must have a negative urine β -HCG pregnancy test at screening and at each visit (except patients who assigned to dose regimen 1 will not attend visits V9 (W10) and V11 (W14), therefore there's no pregnancy test for these patients on both visits). Pregnancy will lead to definitive treatment discontinuation in all cases.
- b Emollients should NOT be applied from Day -7 to the EoS (Week 28) to the targeted, predefined skin areas that will be used for TEWL assessment. Participants should not take showers or soaking in a bathtub within 6 hours before TEWL assessment. Emollients for use during the study will be provided by the study site to study participants. Use of emollients should be documented in a diary provided by the study site.

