8.3 APPENDIX C SCHEDULE OF ACTIVITIES IN HEALTHY VOLUNTEERS

Table 2 - Schedule of activities in healthy volunteers

Phase	Screening	Baseline									EoT	Follow-up period		Unscheduled visit	Premature EoT
Day	D-28 to D-1	D 1	D8 ± 2 days	D15 ± 2 days	D22 ± 2 days	D29 ± 2 days	D43 ± 2 days	D57 ± 3 days	D85 ± 3 days	D113 ± 3 days	D155 ± 3 days	EoS D197 ± 3 days			
Week		W0	W1	W2	W3	W4	W6	W8	W12	W16	W22	W28			
Visits	V01	V02	V03	V04	V05	V06	V07	V08	V09	V10	V11	V12			
Informed consent/assent form	X														
Inclusion/exclusion criteria	X	X													
Matching by age (± 2 years) and gender	X														
Medical/surgical history/demographics	X														
Pregnancy test (urine), WOCBP only ^a	X	X	X	X	X	X	X	X	X	X	X	X			
Prior/concomitant medications/procedure	X	X	X	X	X	X	X	X	X	X	X	X	X	X	X
Confirm emollient and washing compliance ^b	X	X	X	X	X	X	X	X	X	X	X	X	X	X	X
Skin barrier function test in predefined normal skin															
TEWL before STS ^{c, d}		X	X	X	X	X	X	X	X	X	X	X	X	X	X
TEWL and STS assessment ^d		X ^e		X ^e		X ^e		X ^e	X ^e	X ^e	X ^e	X ^e	X ^f	X ^f	
Lipidomics, proteomics, FLG breakdown products and transcriptomics		X ^e		X ^e		X ^e		X ^e	X ^e	X ^e	X ^e	X ^e	X ^f	X ^f	

Phase	Screening	Baseline									EoT	Follow-up period		Unscheduled visit	Premature EoT
Day	D-28 to D-1	D 1	D8 ±2 days	D15 ±2 days	D22 ±2 days	D29 ±2 days	D43 ±2 days	D57 ±3 days	D85 ±3 days	D113 ±3 days	D155 ±3 days	EoS D197 ±3 days			
Week		W0	W1	W2	W3	W4	W6	W8	W12	W16	W22	W28			
Visits	V01	V02	V03	V04	V05	V06	V07	V08	V09	V10	V11	V12			
assessment from skin tape strips ^e															
Standardized photographs of healthy skin area used for TEWL		X	X	X	X	X	X	X	X	X	X	X	(X)	X	
Standardized full body photographs		X	X	X	X	X	X	X	X	X	X	X	(X)	X	
Optical Coherence Tomography (OCT) ^g		X	X	X	X	X	X	X	X	X		X	(X)	X	
Fourier-Transform Infrared (FTIR) Spectroscopy ^g		X						X		X		X	(X)	X	
Safety															
AE/SAE collection	X	X	X	X	X	X	X	X	X	X	X	X	X	X	
Height		X								X		X		X	
Body weight	X	X								X		X		X	
Vital signs ^h	X	X						X		X				X	
Physical examination ⁱ	X	X ⁱ								X ⁱ		X ⁱ		X ⁱ	
Saliva swab sample ^j		X													
Optional assessments															
Biomarker research samples (blood) ^k		X								X					

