8.4 APPENDIX D POTENTIALLY CLINICALLY SIGNIFICANT ABNORMALITIES (PCSA) CRITERIA

Table 3 - PCSA criteria for vital signs parameters for studies in children (24 May 2014)

CRITERIA for POTENTIALLY CLINICALLY SIGNIFICANT ABNORMALITIES For Studies in Children			
Parameter	Age range	PCSA	Comments
Vital Signs			Ref. : Kidney Disease Outcomes Quality Initiatives (KDOQI) Guideline 13; 1996; The fourth report on the diagnosis, evaluation, and treatment of high blood pressure in children and adolescents, Pediatrics 2004; Bowman E & Fraser S Neonatal Handbook 2012; Mulberg AE et al. Pediatric Drug Development Concepts and applications. John Wiley & sons, Inc. 2009; Pediatric respiratory rates http://www.health.ny.gov/
SBP	6 to <12 years old (Children)	≤ 80 mmHg and decrease from baseline ≥ 20 mmHg ≥ 108 mmHg and increase from baseline ≥ 20 mmHg	Based on definition of Hypertension as average SBP or DBP $\geq 95^{\text{th}}$ percentile for gender, age, and height on ≥ 3 occasions
	12 to 16/18 years old (Adolescents)	≤ 90 mmHg and decrease from baseline ≥ 20 mmHg ≥ 119 mmHg and increase from baseline ≥ 20 mmHg	
DBP	6 to <12 years old (Children)	≤ 48 mmHg and decrease from baseline ≥ 10 mmHg ≥ 72 mmHg and increase from baseline ≥ 10 mmHg	
	12 to 16/18 years old (Adolescents)	≤ 54 mmHg and decrease from baseline ≥ 10 mmHg ≥ 78 mmHg and increase from baseline ≥ 10 mmHg	
Temperature	All age ranges	Rectal, ear or temporal artery: ≥ 100.4 °F/38.0 °C Oral or pacifier: ≥ 99.5 °F/37.5 °C Axillary or skin infrared: ≥ 99 °F/37.2 °C	Ear temperature not accurate below 6 months of age
Respiratory rate	6 to <12 years old (Children)	<18 per minutes >30 per minutes	Based on normal range
	12 to 16/18 years old (Adolescents)	<12 per minutes >20 per minutes	
Weight	All ranges	≥ 5 % weight loss from baseline	Based on identification of trends in the child's growth with a series of visits WHO Multicentre Reference Study Group, 2006; Center for Disease Control. Growth chart 2007

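### By-cohort counts of participants with an abnormal (PCSA) vital sign rest on about five scheduled checks in patients and two in healthy volunteers, so the side-by-side table is unbalanced; for weight the imbalance reverses

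*SAP*

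**What the plan says.** Section 4.3.5.2 sets the rule for vital-sign abnormalities: "analysis will be performed using all post-baseline assessments done during the TEAE period/safety period, including all unplanned and rechecked values". The output is then fixed: "Counts of participants with potentially clinically significant abnormal (PCSA) values will be presented by cohort, regardless of the baseline status". A participant therefore counts once if any qualifying value meets a criterion. A listing of participants with post-baseline PCSAs, with the values flagged, is also planned. The descriptive statistics for heart rate, blood pressure, temperature and respiratory rate are planned for the patient cohort only; those for body weight are by cohort.

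Section 4.3.5.1 gives the windows. For patients, the TEAE period runs from first dose through the EoT visit at Week 16. Volunteers' safety data are "considered as part of a single period starting with the signature of the informed consent and ending with the EoS visit", which is Week 28.

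Appendix D gives PCSA limits for systolic and diastolic blood pressure, temperature, respiratory rate and weight. It gives none for heart rate. For ages 6 to under 12, the blood-pressure criteria combine a level with a change from baseline of at least 20 mmHg (systolic) or 10 mmHg (diastolic). Respiratory rate ("<18 per minutes" or above 30) and temperature are judged on level alone. Weight is judged on a loss of at least 5% from baseline.

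**The concern.** The chance that a child has at least one flagged value rises with the number of values taken. The schedules give patients more vital-sign checks than volunteers, and the SAP has no restriction to common visits, no rate per assessment and no caveat. Two cohorts with the same physiology would then be expected to show different counts.

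For blood pressure, temperature and respiratory rate, the PCSA count is the only by-cohort summary that Section 4.3.5.2 specifies. No neighbouring by-cohort table of means would show a reader that an excess came from the number of checks. Only the patient cohort receives dupilumab, so the excess could be taken for an effect of drug or disease.

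**Working it through.** **Inputs from the SAP**

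- Volunteers, Appendix C vital-signs row: Screening, Day 1, Week 8, Week 16 and premature EoT. That is two scheduled post-baseline checks, with none at Week 22 or Week 28.
- Patients, Appendix B vital-signs row: after Screening and Day 1 there are six scheduled marks, then a bracketed mark and the premature EoT mark. Read by position, the six fall at Weeks 2, 4, 6, 8, 14 and 22. The row is displaced in the extracted text: its bracketed mark falls under Week 28, whereas the EASI row has it under the unscheduled visit. If the late marks move one column right, the last two become Weeks 16 and 28. Either way five fall by Week 16. If Week 14 is right, regimen 1 patients, who do not attend that visit (Appendix B, footnote a), have four.
- Weight: Week 16 and Week 28 in both schedules. The patient window ends at Week 16 (one check) and the volunteer window at Week 28 (two checks).
- Cohort size: the SAP gives no figure for PCSA counts. Its only relevant number is the 24 in Section 1.3, which is reproduced: 20 / (1 − 0.15) = 23.5, rounded up to 24.

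**Assumptions (not in the SAP)**

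The per-check chance p of meeting a criterion is the same in both cohorts, so the true difference is zero. The range tried is 1% to 20%.

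**Independent checks**

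P(at least one PCSA in k checks) = 1 − (1 − p)^k. For p = 0.05: patients 1 − 0.95^5 = 0.226; volunteers 1 − 0.95^2 = 0.0975. Multiplying by 24 gives the expected counts.

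| p | Patients, k = 5 | Volunteers, k = 2 | Ratio | Expected of 24 |
|---|---|---|---|---|
| 0.01 | 4.9% | 2.0% | 2.46 | 1.2 vs 0.5 |
| 0.05 | 22.6% | 9.8% | 2.32 | 5.4 vs 2.3 |
| 0.10 | 41.0% | 19.0% | 2.16 | 9.8 vs 4.6 |
| 0.20 | 67.2% | 36.0% | 1.87 | 16.1 vs 8.6 |

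With four patient checks and p = 0.05: 1 − 0.95^4 = 18.5%, ratio 1.90.

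**Correlated checks within a child, p = 0.05**

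Under a beta-binomial model with correlation ρ between the flags, let s = (1 − ρ)/ρ and b = (1 − p)s. Then P(no flag in k checks) is the product over i = 0 to k − 1 of (b + i)/(s + i).

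- ρ = 0.5: s = 1, b = 0.95. Two checks: 1 − (0.95 × 1.95)/(1 × 2) = 7.4%. Five checks: 11.0%. Ratio 1.49.
- ρ = 0.7: 8.3% vs 6.4%, ratio about 1.29.
- ρ = 1: 5.0% in both, ratio 1.00.

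If the correlation is placed on a latent normal scale instead, the figures are 16.6% vs 8.7% at 0.5 (ratio 1.9) and 13.5% vs 8.0% at 0.7 (ratio 1.7).

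**Realised counts**

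With 24 per cohort and 5 vs 2 independent checks, the patient count is actually the larger with probability 0.54 (p = 0.01), 0.85 (p = 0.05) or 0.94 (p = 0.10).

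**Weight**

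With one patient check and two volunteer checks at p = 0.05 (independent): 5.0% vs 9.8%, or 1.2 vs 2.3 of 24. The volunteers are now the cohort with the inflated expectation.

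**After the fix**

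With two common checks per child, both cohorts have 1 − 0.95^2 = 9.8% (2.3 of 24) at p = 0.05 and 19.0% (4.6 of 24) at p = 0.10. The built-in gap is gone.

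**The case against.** The best defence is that no safety comparison between cohorts is intended. The volunteers are a reference for skin barrier function; TEAE summaries and most vital-sign statistics are for patients only; Section 5.6 predefines no hypothesis test; and by-cohort display follows the general convention in Section 4.3.5. Counting every value, rechecks included, is a normal conservative safety rule, and the listing lets a careful reader trace each flag. This stands as far as it goes: the table is descriptive and no decision hangs on it. But the SAP still sets the two counts beside each other without the number of checks behind them.

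The size is also assumed. The SAP gives neither a per-check probability nor a correlation. A child whose resting respiratory rate stays near the limit would be flagged repeatedly, which pulls the ratio towards 1. That stands, and it is why the lower end is put at about 1.3. The two-part blood-pressure criteria make a flag less likely per reading, but one post-baseline reading set against the child's baseline can still meet both parts, so the mechanism remains.

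A reader might infer more than the SAP supports:

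- That the patient count must come out higher. This holds for the expected count only.
- That it holds for every PCSA parameter. Weight runs the other way.
- That the longer volunteer window adds to the patient excess. It brings volunteers no further scheduled vital-sign check and, through unplanned values, can only raise their count.
- That a false-positive rate is affected. No test is planned.

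Finally, Week 16 as a patient vital-sign visit depends on reading a displaced row, and this must be settled before it is named as a common visit.

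**Conclusion.** The point holds in this limited form. For systolic and diastolic blood pressure, temperature and respiratory rate, the planned by-cohort count has a higher expected value in patients when there is no true difference, because about five scheduled checks (at least four) are set against two. At an assumed 5% per check the gap is 22.6% against 9.8% with independent checks, a ratio of 2.3. With strong within-child correlation of the flags the ratio is about 1.3 to 1.5, and it vanishes only at perfect correlation. For weight the difference in windows gives volunteers two checks and patients one. The number of patient checks survives the damage to the Appendix B row; their exact weeks do not. The consequence is a side-by-side table that can mislead in either direction, depending on the parameter. It is a modest fault in an exploratory study, worth correcting because correction is cheap.

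**What to change.** In Section 4.3.5.2:

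1. Base the by-cohort PCSA counts on scheduled post-baseline assessments common to both cohorts, within one window, Day 1 to Week 16. Use Weeks 8 and 16 for vital signs and Week 16 for weight.
2. First confirm the patient vital-sign visits against the original Appendix B. Week 8 is marked in both schedules as they read here; Week 16 for patients needs the check.
3. Keep the all-values count, with unplanned and rechecked values, and the listing for the patient cohort.
4. If an all-values count is also shown by cohort, print the number of assessments per participant beside it.

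The cost is a change of SAP wording and one extra table from data already collected. The common-visit count ignores the patients' other visits, which stay in the patient-only count and the listing. Patients will then have two PCSA counts, so each must be labelled with the visits and window it uses.

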4.3.5.3 Clinical laboratory parameters

Positive results as well as all individual data for urine pregnancy tests (for women with childbearing potential only) will be listed.

5 DATA HANDLING CONVENTIONS

5.1 DATA HANDLING CONVENTIONS FOR PATIENT DATA

In all tables, figures, listings and in-texts, the following cohort labels will be used:

- Healthy Participant.
- AD Participant.

5.2 DATA HANDLING CONVENTIONS FOR PATIENT REPORTED OUTCOMES

When multiple answers are reported by the patient, the data will be considered as missing.

5.3 MISSING DATA

Missing data imputation (last observation carried forward (LOCF) method or another complex method) could be envisaged due to a high number of missing data and high variability. Sensitivity analyses could also be planned.

5.4 DEFINITION OF REGIONS

Not applicable.

5.5 WINDOWS FOR TIME POINTS

Except for the baselines, only observations from visits and/or timepoints planned in the protocol will be used in descriptive statistics. Usually, all timepoints planned in the protocol should be described.

All the data collected from eDiary (Patient-reported outcome) were linked to a unique unscheduled visit in the SDTM database. To perform the analysis by visit, the following visit window algorithm is defined.

VISIT WINDOW ALGORITHM		
Patient-Reported Outcomes	Planned visits in the protocol	Time interval for analysed visits
Worst itch NRS	D1	-1 to 1 day before the first IMP administration
Sleep disturbance NRS	From D2 to D28	x days after the first IMP administration for each Dx
Skin pain NRS	D36	29 to 39 days after the first IMP administration

VISIT WINDOW ALGORITHM		
Patient-Reported Outcomes	Planned visits in the protocol	Time interval for analysed visits
	D43	40 to 50 days after the first IMP administration
	D57	51 to 71 days after the first IMP administration
	D85	72 to 99 days after the first IMP administration
	D113	100 to 134 days after the first IMP administration
	D155	135 to 176 days after the first IMP administration
	D197	177 to 200 days after the first IMP administration

If more than one record occurs within the same visit window where only one assessment is expected, then the following rule will be applied: for D1, the last non-missing result prior to study drug administration will be used; for post-treatment assessments the closest non-missing result to the scheduled visit will be used.

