4.3.2.2 Baseline efficacy parameters

For efficacy parameters, baseline is defined as the last available and evaluable value at Day 1 (Week 0) (or at Screening if the value at Day 1 is not available) for patients and healthy volunteers.

For TEWL data, the baseline value will be defined for each skin group and each number of STS (before/without STS, after 5 STS, after 10 STS, after 15 STS and after 20 STS). In addition for before/without STS, a baseline will be defined for each spot, due to strong variability between the 3 adjacent spots in a similar study conduct by the Sponsor.

Baseline efficacy values will be presented along with the subsequent efficacy values assessed during the on-treatment period.

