- c Dose regimen 1: Children with baseline $15 \text{ kg} \leq \text{body weight} < 30 \text{ kg}$ will receive a SC loading dose of dupilumab 600 mg (2 injections of dupilumab 300 mg) on Day 1 (V02), followed by every 4-week SC dosing of dupilumab 300 mg until Week 12 (at Week 0 [(Day 1], Weeks 4, 8, and 12).
- Dose regimen 2: Children with baseline $30 \text{ kg} \leq \text{body weight} < 60 \text{ kg}$ will receive a SC loading dose of dupilumab 400 mg (2 injections of dupilumab 200 mg) on Day 1 (V02), followed by bi-weekly SC dosing of dupilumab 200 mg until Week 14 (at Week 0 (Day 1), Weeks 2, 4, 6, 8, 10, 12, and 14).
- d Assessments on treatment days have to be conducted before administration of dupilumab.
- e Predefined lesional and non-lesional skin areas. TEWL will be measured at each of the 3 closely adjacent spots within the predefined skin areas at all visits without STS and before STS at visits with STS.
- f TEWL will be conducted before STS and then after 5, 10, 15, and 20 STS in lesional skin and non-lesional skin.
- g At Weeks 0, 8, 16, and 28, STS will be conducted on the first spot within the predefined skin area. At Week 2 STS will be conducted on the second spot within the predefined skin area. At Weeks 4, 12, and 22 STS will be conducted on the third spot within the predefined skin area. TEWL will be assessed in lesional skin and non-lesional skin before STS and after 5, 10, 15, and 20 STS. All skin tape strips should be collected and stored.
- h In case STS assessment is to be conducted at an unscheduled visit or at a premature EoT visit the assessment should be conducted at that spot of the skin area, for which the period passed since the last STS assessment is the longest.
- i OCT will be done before STS/TWL, and FTIR will be done before and during STS.
- j Worst itch NRS, Sleep disturbance NRS and Skin pain NRS will be assessed daily from Day -7 to Day -1; daily from Day 1 to Week 4 and then 7 days prior to Week 6, Week 8, Week 12, Week 16, Week 22, and to Week 28 by e-diary.
- k eDiary will be dispensed to the patients at screening (Visit 01) and will be collected on Week 28 (Visit 14). The PROs will be administered to patients via eDiary. Patients will bring the eDiary to the site at each visit, and it will be reviewed for any questionnaires omission and dispensed back to patients at each visit.

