- Change (percent and absolute) in photograph outputs (eg, severity score) obtained from skin imaging over time.
- Correlation between baseline values of TEWL before and after STS, and TEWL AUC in lesional and non-lesional skin of AD patients with the following baseline measures:
 - EASI, Targeted lesion ISS, PRO measures (POEM, CDLQI, worst itch numerical rating scale (NRS), sleep disturbance NRS, and skin pain NRS), Lipidomics in STS (ratio of EOS CER to NS CER), FLG breakdown products of Urocanic Acid (UCA) and Pyroglutamic Acid (PCA) concentrations in STS, Image-derived severity score in targeted lesional skin, Key components of skin proteomics in STS (expression of proteins associated with skin barrier function), Quantified epidermal hypertrophy and structure changes in OCT and FTIR measures, Key components of gene expression from transcriptomics.
- Correlation between percent change from baseline in TEWL before and after STS, and TEWL AUC in lesional and non-lesional skin of AD patients at Week 8, Week 16 and Week 28 with corresponding change from baseline in the following measures:
 - EASI, Targeted lesion ISS, PRO measures (POEM, CDLQI, worst itch NRS, sleep disturbance NRS, and skin pain NRS), Lipidomics in STS (ratio of EOS CER to NS CER), FLG breakdown products of UCA and PCA concentrations in STS, Image-derived severity score in targeted lesional skin, Key components of skin proteomics in STS (expression of proteins associated with skin barrier function), Quantified epidermal hypertrophy and structure changes in OCT and Fourier-transform infrared (FTIR) measures, Key components of gene expression from transcriptomics.

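### Itch, sleep and pain NRS (tertiary): baseline uses one diary score although seven daily scores are collected; averaging them is a cheap, low-stakes gain in precision

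*SAP*

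**What the plan says.** **Collection.** Footnote j to the patient schedule (clinical SAP, section 8.2) states: "Worst itch NRS, Sleep disturbance NRS and Skin pain NRS will be assessed daily from Day -7 to Day -1". Scoring continues daily from Day 1 to Week 4, "then 7 days prior to Week 6, Week 8, Week 12, Week 16, Week 22, and to Week 28". The word for daily is not repeated in that last clause.

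**Baseline.** Section 4.3.2.2 sets one rule for all efficacy parameters: "baseline is defined as the last available and evaluable value at Day 1 (Week 0"), with screening as fallback. In the section 5.5 table the D1 row runs from minus "1 to 1 day before the first IMP administration", and where several records fall in it, "for D1, the last non-missing result prior to study drug administration will be used".

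**Later visits.** Section 5.5 adds that "for post-treatment assessments the closest non-missing result to the scheduled visit will be used". The rule is worded for windows in which a single assessment is expected. The D36 row covers 29 to 39 days, the D43 row "40 to 50 days after the first IMP administration", and the D57 row 51 to 71 days.

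**Use.** The three NRS are tertiary endpoints (section 4.1.4) and are summarised descriptively (section 4.3.3.3). No hypothesis test is predefined (section 5.6). Neither section 5.5 nor section 4.3.3.3 plans a weekly mean.

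**The concern.** Children are asked for seven consecutive daily scores before dosing, and the analysis keeps one. A single day's itch, sleep or pain score carries day-to-day noise that a weekly mean would reduce, and a noisy baseline enters every change from baseline. If the later diary weeks are also daily, the same loss recurs at the other end of each change. The tie-break rule is also written for one expected record, which does not fit a daily diary.

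What is at stake is the precision of descriptive change summaries for three tertiary scores in about 20 evaluable patients. Section 6 includes these scores in the treatment-phase analysis, so they will be reported, but nothing confirmatory rests on them.

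**Working it through.** **Plan's own figure.** Section 1.3: 20 evaluable patients at 15% drop-out gives 20/0.85 = 23.5, rounded up to 24. This reproduces. The SAP states no figure for NRS precision.

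**Scores collected and used**
- *Baseline:* seven scheduled days (Day -7 to Day -1), plus any Day 1 entry before dosing. One is used.
- *Weeks 12, 16, 22 and 28*, if daily: the diary weeks D78-D84, D106-D112, D148-D154 and D190-D196 each lie wholly inside their own window. One of seven is used.
- *Week 6*, if daily: the table treats Dx as x days after first dose. On that count D36-D39 fall in the D36 row and D40-D42 in the D43 row, so the diary week supplies one score to each of two rows.
- *Week 8*, if daily: D50 falls in the D43 row and D51-D56 in the D57 row.

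If days after dose means day number minus one, the Week 6 and Week 8 splits are 5/2 and 2/5 instead of 4/3 and 1/6. Averaging within the present windows would therefore not give the pre-visit week at Weeks 6 and 8.

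**Daily or once only after Week 4?** If one entry were made 7 days before each visit, the Week 8 entry (D50) would fall in the D43 window and supply nothing to D57. Daily scoring is the likelier reading.

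**Precision.** Assumed inputs, none from the SAP: reliability of a single-day score r = 0.5 to 0.9; correlation of the underlying baseline and later levels c = 0.3 to 0.6; lag-one correlation of day errors 0 to 0.5. Set the single-day variance to 1. Let F be the variance of a 7-day mean error relative to a single-day error:
- Independent errors: F = 1/7 = 0.143.
- Lag-one correlation 0.5: F = [7 + 2(6×0.5 + 5×0.25 + 4×0.125 + 3×0.0625 + 2×0.03125 + 0.015625)]/49 = 17.03/49 = 0.348.

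Variance of change:
- Single days: 2r(1−c) + 2(1−r)
- Baseline averaged: 2r(1−c) + (1−r)(1+F)
- Both ends averaged: 2r(1−c) + 2(1−r)F

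| Case | Single | Baseline averaged | Both averaged | SD ratio, baseline only | SD ratio, both |
|---|---|---|---|---|---|
| r 0.9, c 0.3, F 0.348 | 1.460 | 1.395 | 1.330 | 1.02 | 1.05 |
| r 0.7, c 0.5, F 0.143 | 1.300 | 1.043 | 0.786 | 1.12 | 1.29 |
| r 0.5, c 0.6, F 0.143 | 1.400 | 0.971 | 0.543 | 1.20 | 1.61 |

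With F = 0.348 the middle case gives √(1.300/0.909) = 1.20 for both ends averaged.

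Effective sample size is 20/ratio². Single-day change is as precise as 19.1 down to 13.9 patients with an averaged baseline, or 18.2 down to 7.8 with both ends averaged.

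**Cross-check.** With within-week correlation ρ, baseline-to-visit correlation b and independent day errors, the SE ratio of averaged to single-day change is √{[(1+6ρ)/7 − b]/(1−b)}. At ρ = 0.7 and b = 0.4 this is √(0.343/0.6) = 0.756, or 1.32 when inverted, inside the range above.

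**Cost of a minimum-days rule.** With a 4-of-7 minimum and independent daily completion p, the chance of three or fewer scores is 0.033 at p = 0.8 and 0.126 at p = 0.7.

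**The case against.** The strongest reply is that this is a preference. A last-value baseline with closest-record windows is workable, it matches section 4.3.2.2, and no conclusion depends on the SEM of a tertiary score. That stands, and it sets the weight of the point. It does not remove the point, because the scores are already collected and averaging needs only wording and simple programming.

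Several stronger readings are tempting and are not supported:
- *Footnote j contradicts section 5.5.* It does not. One describes what is collected, the other what is analysed.
- *Six of seven scores are lost at every visit.* Only the baseline count is explicit. After Week 4 it depends on reading the footnote as daily and on applying a rule worded for a single expected record. At Week 6 two rows draw on the diary week.
- *The windows select the wrong week.* With complete diaries they do not: a Week 6 visit at D41 to D45 selects D40 to D43, and a Week 8 visit at D54 to D60 selects D53 to D57. Trouble needs missing late-week entries. The chance that D40-D42 are all missing is 0.2³ = 0.008 at 80% independent completion.
- *NRS-TEWL correlations are weakened.* The biomarker SAP (section 1.3.3) lists correlations of TEWL with "PRO measures (POEM, CDLQI, worst itch numerical rating scale (NRS), sleep disturbance NRS, and skin pain NRS"), but it has its own baseline definition, and its correlation methods (sections 2.4.1 and 2.4.2) do not specify NRS-TEWL pairs. The clinical SAP's correlation list (section 4.3.3.3) omits the NRS, and section 1.5 only allows that PRO correlations might be added. Attenuation is possible, but no specified analysis anchors it.

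A fair criticism of averaging is that single-day D2 to D28 values would sit beside 7-day means in the same profiles, so spread would fall after Week 4 because of the derivation. The fix has to deal with that.

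**Conclusion.** The point holds as a low-stakes, inexpensive improvement. At baseline the loss is explicit: about six of seven scheduled scores are not used. At Weeks 6 to 28 it is conditional on the diary being daily, and section 5.5 should say so either way.

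The gain is positive whenever scores within a week are not perfectly correlated. Its size cannot be fixed from the SAP. On the assumed ranges, the single-day SD of change is 1.02 to 1.20 times that with an averaged baseline, and 1.05 to 1.61 times that with both ends averaged. The upper end needs the lowest reliability, the highest level correlation and independent day errors together, and all figures assume complete diaries. TEWL and every other primary or secondary result are untouched.

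**What to change.** 1. In section 4.3.2.2, add an exception for the three NRS: baseline is the mean of the available Day -7 to Day -1 scores, with a stated minimum (for example 4 of 7). Amend the D1 row and rule in section 5.5 to match.
2. Confirm whether the diary before Weeks 6 to 28 is daily. If it is, define each of those values as the mean of the 7 diary days before the visit, with the same minimum, using diary-week windows for the means (nominally D36-D42 for Week 6 and D50-D56 for Week 8).
3. Keep D2 to D28 as daily values. Keep the D36 row, which section 5.5 lists as planned, unless the protocol shows that it is not a planned timepoint.
4. Retain the single-day derivation as a supportive summary, so that early and late profiles can be compared on one metric.

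The cost is SAP wording and simple programming, with no new data. The downsides are that about 3% of diary weeks would fail a 4-of-7 minimum at 80% completion and 13% at 70%, the NRS baseline would differ from the Day 1 baseline of the other endpoints, and spread would drop after Week 4 in the averaged profiles.
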